Appendix I Dose modifications for the management of adverse events

I 1 Osimertinib dose modification and guidance

Osimertinib management should be in accordance with the local label in the first instance.

If a patient experiences a CTCAE Grade 3 and/or unacceptable toxicity dosing will be interrupted and supportive therapy administered as required in accordance with local practice/guidelines.

If a toxicity resolves or reverts to \leq CTCAE Grade 2 within 3 weeks of onset, treatment with osimertinib may be restarted at the same dose (80 mg) or a lower dose (40 mg) using the rules below for dose modifications ([Table 19](#)) and with discussion and agreement with the AstraZeneca Study Team Physician as needed. There will be no individual modifications to dose regimen in response to toxicity, only potential dose reduction or dose interruption.

If the toxicity does not resolve to \leq CTCAE Grade 2 after 3 weeks, then the patient should be withdrawn from the study and observed until resolution of the toxicity ([Table 20](#)).

Table 19 Dose reduction for osimertinib to manage adverse events

	Starting osimertinib dose 80 mg
Reduced dose -1	40 mg

On resolution of toxicity within 3 weeks:

If an AE subsequently requires dose interruption, osimertinib may restart at the same dose or the reduced dose, on resolution/improvement of the AE at the discretion of the investigator.

Table 20 Osimertinib Dose Adjustment Information for Adverse Reactions

Target organ	Adverse reaction ^a	Dose modification
Pulmonary	ILD/pneumonitis	Permanently discontinue osimertinib
Cardiac	QTc interval > 500 msec on at least 2 separate ECGs	Withhold osimertinib until QTc interval is < 481 msec or recovery to baseline if baseline QTc is ≥ 481 msec within 3 weeks of interruption, then restart at a reduced dose (40 mg) or at 80 mg (at the discretion of the investigator), to allow for situations where causality in relation to osimertinib may be difficult to determine.
	QTc interval prolongation with signs/symptoms of serious arrhythmia, symptomatic congestive heart failure	Permanently discontinue osimertinib
Other	Grade ≥ 3 adverse reaction	Withhold osimertinib for up to 3 weeks
	If Grade ≥ 3 adverse reaction improves to Grade 0 – 2 after withholding osimertinib for up to 3 weeks	Osimertinib may be restarted at the same dose (80 mg) or at a lower dose (40 mg)
	Grade ≥ 3 adverse reaction that does not improve to Grade 0 – 2 after withholding osimertinib for up to 3 weeks	Permanently discontinue osimertinib

^a The intensity of the clinical adverse events graded by the NCI CTCAE version 5.0.

CTCAE Common Terminology Criteria for Adverse Events; ECG Electrocardiogram; ILD Interstitial lung disease; NCI National Cancer Institute.

I 1.1 ILD/Pneumonitis-like toxicity

If new or worsening pulmonary symptoms (eg, dyspnoea) or radiological abnormality suggestive of ILD is observed, an interruption in study treatment dosing is recommended, and the AstraZeneca study team should be informed. It is strongly recommended to perform a full diagnostic workup, to exclude alternative causes such as lymphangitic carcinomatosis, infection, allergy, cardiogenic oedema or pulmonary haemorrhage. The results of full diagnostic workup (including high resolution computed tomography (HRCT), blood and sputum culture, haematological parameters) will be captured by eCRF. All image data should be provided to AstraZeneca. In the presence of confirmatory HRCT scans where other causes of respiratory symptoms have been excluded, a diagnosis of interstitial lung disease should be considered and study treatment permanently discontinued.

I 1.2 QTcF prolongation

In light of the potential for QT changes associated with osimertinib, and in accordance with good clinical practice, it is recommended that correction of clinically significant electrolyte

abnormalities (hypokalaemia, hypomagnesaemia, hypocalcaemia) to within normal ranges takes place prior to first dose and during study treatment with osimertinib.

Table 21 Dose Modifications for Osimertinib-Related QTc Prolongation

NCI CTCAE version 5 toxicity grade	Action
Grade 0, 1, or 2	None
Grade 3	
Hold dosing and follow algorithm below
 
Patients with QTcF prolongation to > 500 msec on at least 2 separate ECGsIf the toxicity does not resolve to QTcF < 481 msec within 21 days
Grade 4	
QTcF \geq 501 or > 60 msec change from baseline and Torsade de pointes or polymorphic ventricular tachycardia or signs/symptoms of serious arrhythmia 
Discontinue osimertinib and consult with a cardiologist for further management as clinically indicated

CTCAE = Common Terminology Criteria for Adverse Events; ECG = Electrocardiogram; NCI = National Cancer Institute; QTcF = QT corrected according to Fridericia's formula.

I 1.3 Keratitis

Patients presenting with signs and symptoms suggestive of keratitis such as acute or worsening: eye inflammation, lacrimation, light sensitivity, blurred vision, eye pain and/or red eye should be referred promptly to an ophthalmology specialist.

I 1.4 Erythema Multiforme and Stevens-Johnson syndrome

Case reports of Erythema multiforme (EM) and Stevens-Johnson syndrome (SJS) have been uncommonly and rarely reported, respectively, in association with osimertinib treatment.

Before initiating treatment, patients should be advised of signs and symptoms of EM and SJS. If signs and symptoms suggestive of EM develop, close patient monitoring and drug interruption or discontinuation of osimertinib should be considered. If signs and symptoms suggestive of SJS appear, osimertinib should be interrupted or discontinued immediately.

I 1.5 Changes in cardiac contractility

Based on the available clinical trial data, a causal relationship between effects on changes in cardiac contractility and osimertinib has not been established. In patients with cardiac risk factors and those with conditions that can affect left ventricular ejection fraction (LVEF),

cardiac monitoring, including an assessment of LVEF at baseline and during treatment, should be considered. In patients who develop relevant cardiac signs/symptoms during treatment, cardiac monitoring including LVEF assessment should be considered.

I 1.6 Permanent discontinuation due to toxicity

Patients experiencing ILD or QTcF prolongation with signs/symptoms of serious arrhythmia will not be permitted to restart study treatment.

I 1.7 Aplastic anaemia

Rare reports of aplastic anaemia have been reported in association with osimertinib treatment. Some cases had a fatal outcome. Before initiating treatment, patients should be advised of signs and symptoms of aplastic anaemia including but not limited to persistent fever, bruising, bleeding, and/or pallor. If signs and symptoms suggestive of aplastic anaemia develop, close patient monitoring and drug interruption or discontinuation of osimertinib should be considered. Osimertinib should be discontinued in patients with confirmed aplastic anaemia.

I 2 Hepatitis B viral reactivation management guideline

In patients with resolved or chronic hepatitis B infection (inactive carrier state) or active controlled HBV infection on treatment with osimertinib:

- Recommend monthly monitoring of ALT/AST, HBV DNA levels and HBsAg (if negative at baseline)
- Where liver signs and symptoms of viral reactivation appear (HBV DNA levels exceeding 10-fold from baseline or ≥ 100 IU/ml (if baseline HBV DNA levels are undetectable) or conversion of HBsAg negative to positive):
 - Expert hepatologist/specialist oversight of the patient is required
 - Consider interruption or discontinuation of study treatment, based on risk-benefit assessment

I 3 Savolitinib dose modification and guidance

I 3.1 Savolitinib dose modification and guidance

Substantial acute toxicities should be managed as medically indicated and with temporary suspension of savolitinib, as appropriate unless due to suspected hypersensitivity (See section I 2.4).

Dose reductions or holds are allowed as clinically indicated by the treating physician and in line with [Table 22](#) and [Table 23](#). For each patient, a maximum of 2 dose reductions of

savolitinib will be allowed. No dose re-escalations are allowed. Guidance on dose level reduction is presented in [Table 22](#).

Table 22 Dose reduction for savolitinib to manage adverse events

Starting savolitinib dose	300 mg bid	300 mg od	600 mg od
Reduced dose -1	CCI	CCI	CCI
Reduced dose -2	CCI	CCI	CCI

Note: Only 2 dose reductions of savolitinib are permitted.

I 3.2 Dose modifications due to savolitinib-related toxicity

Dose modification guidelines for general savolitinib-related toxicities are shown in [Table 23](#) below. Appropriate and optimal treatment of the toxicity is assumed prior to considering dose modifications. Prior to discontinuation of savolitinib due to toxicities please consult with the study physician. Please see Section [I 3.3](#) for hepatotoxicity management guidelines and Section [I 3.4](#) for management of savolitinib specific toxicities including dermatologic toxicity, hypersensitivity, and QTc prolongation.

Table 23 Dose modifications for savolitinib-related toxicities

NCI CTCAE version 5.0 toxicity grade	Action
Grade 0, 1 or 2	None
Grade 3 ^a 
 Grade 3 toxicity for ≤ 7 days. Grade 3 toxicity for >7 days. 	Hold dosing and follow algorithm below 
 Resume dosing at same dose or 1 reduced dose level (maximum of 2 dose reductions) as clinically appropriate^b Discontinue study drug
Grade 4 
 Expected to be manageable/reversible with dose reduction Not expected to be manageable/reversible with dose reduction 	
 Hold dose and consult with study medical monitor Discontinue study drug
Recurrence of Grade 3 
 Grade 3 toxicity for ≤ 7 days. Grade 3 toxicity for >7 days. 	
 Resume dosing at same dose or 1 reduced dose level (maximum of 2 dose reductions) as clinically appropriate^b Discontinue study drug
Recurrence of Grade 4	Discontinue study drug

^a Despite appropriate supportive care.

^b Restart of savolitinib must follow the specific restart guidelines if the event includes symptoms of pyrexia, skin reactions, myalgia, arthralgia, or hypersensitivity, as per section [I 3.4](#)

No more than 2 dose reductions of savolitinib will be allowed for any patient. Patients requiring additional dose modifications due to toxicity will discontinue savolitinib.

I 3.3 Hepatotoxicity management guideline

- Promptly evaluate patients with elevated LFTs during study treatment for alternative aetiologies and potential Hy's law criteria, and discontinue potential contributing concomitant medications or alternative causal agents, as well as anti-coagulants, if appropriate.
- If a patient discontinues due to LFT abnormality, LFT monitoring should continue until resolved to Grade 1 or baseline or an apparent plateau has been reached.

I 3.3.1 Dose modification due to drug-related hepatotoxicity

- Permanently discontinue drug if:
 - ALT or AST $>8 \times$ ULN with total bilirubin elevation above baseline or ULN, or
 - ALT or AST $>5 \times$ ULN for up to 1 week (<7 days) with total bilirubin elevation above baseline or ULN, following immediate withholding of savolitinib. Repeat LFT testing within 2 to 3 days and at least twice a week until improvement to Grade 1 or baseline.
 - ALT or AST $>3 \times$ ULN and (total bilirubin $>2 \times$ ULN or INR >1.5 if not on anticoagulants that elevate the INR), or
 - AST or ALT $>3 \times$ ULN with the appearance of fatigue, nausea, vomiting, right upper quadrant pain or tenderness, fever, rash and/or eosinophilia $>5\%$
- Withhold dosing if ALT or AST $>5 \times$ ULN for > 2 weeks or $8 \times$ ULN without total bilirubin elevation above baseline or ULN, repeat LFT testing twice a week for 1 week:
 - If improved to Grade 1 or baseline in 1 week, resume at reduced dose with LFT testing twice a week for 6 weeks
 - If not, discontinue
- Withhold dosing if ALT or AST $>3 \times$ ULN and concurrent total bilirubin $>1.5 \times$ ULN, repeat LFT testing twice a week for 1 week:
 - If both ALT/AST and total bilirubin improved to Grade 1 or baseline in 1 week, resume at reduced dose with LFT testing twice a week for 6 weeks
 - If not, discontinue
- Withhold dosing if ALT or AST $>3 \times$ ULN and concurrent total bilirubin $>1 \times$ ULN to $1.5 \times$ ULN. Repeat LFT testing twice a week for 1 week:
 - If both ALT/AST and total bilirubin improve to normal range (< Grade 1) or baseline in 1 week, resume at same dose with LFT testing twice a week for 6 weeks
 - If not, resume at reduced dose, (as per bullet 3 above).
- Continue dosing if ALT or AST $>3 \times$ ULN without total bilirubin elevation above baseline or ULN, repeat LFT testing every week

- If ALT or AST trending upward, withhold dosing and repeat LFT twice a week for 1 week
- If improve to Grade 1 or baseline in 1 week, resume at same dose with LFT testing every week for 6 weeks
- If improve to Grade 1 or baseline in 2 weeks, resume at reduced dose with LFT testing every week for 6 weeks
- If not, discontinue
- Discontinue for recurrent ALT or AST $>5 \times$ ULN
- Discontinue for recurrent ALT or AST $>3 \times$ ULN and total bilirubin $>1.5 \times$ ULN
- Withhold dosing for recurrent ALT or AST $>3 \times$ ULN without total bilirubin elevation above baseline or ULN, repeat LFT testing twice a week for 1 week
 - If improve to Grade 1 or baseline in 1 week, resume at reduced dose with LFT testing every week for 6 weeks; if not, discontinue

I 3.4 Guidance for management of savolitinib specific toxicities

Dermatologic: A case of Stevens-Johnson syndrome (SJS) has been reported in temporal association with savolitinib. Patients who show symptoms or signs suggesting emerging SJS while on study treatment (eg, progressive skin rash often with blisters or mucosal lesions), must discontinue savolitinib immediately and receive appropriate treatment. If emerging SJS is suspected, re-challenge with savolitinib must be avoided.

Hypersensitivity: Hypersensitivity, which may manifest as a constellation of symptoms such as but not limited to pyrexia, allergic skin reaction, increased liver enzymes, cytopenia, or myalgia and/or arthralgia has been reported after savolitinib dosing. These reactions have occurred within days to weeks after the first dose but the majority of reactions have occurred in the first six weeks of therapy. Patients with suspected savolitinib-related hypersensitivity (excluding confirmed infective aetiology), may be managed with corticosteroids, antihistamines and antipyretics (doses and duration of treatment according to local practice at the discretion of the investigator). Dose interruption with savolitinib should be avoided, if possible. Some patients who experienced the initial hypersensitivity reaction also reported severe acute hypersensitivity reactions, including anaphylaxis, upon restarting savolitinib treatment following a short period of interruption. If patients do need dose interruption, restarting savolitinib must be done under controlled conditions as per below. If the patient experiences an acute hypersensitivity or anaphylactic reaction, immediate intervention must be instituted and treatment with savolitinib should be permanently discontinued.

Restarting savolitinib: acute hypersensitivity including anaphylaxis has been observed in a number of patients mostly upon savolitinib restart. If interruption of savolitinib occurs in the first 6 weeks of study treatment due to savolitinib-related general toxicities, or specific

hypersensitivity toxicities occur at any time, dosing with savolitinib may be resumed but at a reduced dose, only after consultation with and approval from the study physician and with the following management:

- Treatment:
 - Pre-treatment with systemic corticosteroids must be started **at least** 24 hours before the restart of savolitinib;
 - Pre-treatment with antipyretics and antihistamines on the day of restart of savolitinib;
 - Doses of antihistamines, corticosteroids and antipyretics should be according to labelling instructions/product information.
 - These medications must be continued daily until discontinuation of savolitinib, but doses of steroids may subsequently be tapered according to local practice
- Intense medical monitoring (restart at the institution):
 - The restart of savolitinib must be performed in the hospital/institution where the clinical study is carried out with medical equipment readily available for resuscitation and management of anaphylaxis
 - Vital status recording (blood pressure, temperature, respiratory rate, heart rate, etc.) before administration of study drug, every 15 mins after savolitinib dosing for the 1st hour, every 30 mins for the next hour and hourly for a total of at least 4 hours.
 - Patient must be observed in the clinic for 24 hours before discharge.
 - Should the symptoms recur, or an acute anaphylactic reaction occurs, immediate intervention must be instituted for appropriate management of event and savolitinib must be permanently discontinued.

Any recommendations regarding hypersensitivity management or pre-treatment should be used as guidelines only. Final decisions concerning management of individual patients reside with the investigator or the treating physician.

QTc prolongation:

Table 24 Dose modifications for savolitinib-related QTc prolongation

NCI CTCAE version 5.0 Toxicity Grade	Action
Grade 0, 1, or 2	None
Grade 3 
• Patients with QTcF prolongation to >500 msec on at least 2 separate ECGs	Hold dosing and follow algorithm below: 
• Consult with cardiologist to validate ECG finding. Ensure cardiac surveillance and take actions in accordance with clinical standards. Regular ECGs performed until resolution to QTcF <481 msec and then restart drug at one reduced dose level

Table 24 Dose modifications for savolitinib-related QTc prolongation

NCI CTCAE version 5.0 Toxicity Grade	Action

 If the toxicity does not resolve to QTcF <481 msec within 21 days 	
 Discontinue study drug and consult with a cardiologist for further management as clinically indicated
Grade 4 
 QTcF \geq501 or >60 msec change from baseline and Torsade de pointes or polymorphic ventricular tachycardia or signs/symptoms of serious arrhythmia 	
 Discontinue study drug and consult with a cardiologist for further management as clinically indicated

CTCAE Common Terminology Criteria for Adverse Events; ECG Electrocardiogram; NCI National Cancer Institute; QTcF corrected QT interval using Fridericia's formulas.

I 3.5 Guideline for the Management of Overlapping Toxicities Between Osimertinib and Savolitinib

QTc Prolongation

QT prolongation is a recognised toxicity of osimertinib and savolitinib; management of this toxicity is summarised in [Table 25](#).

Table 25 Management of QTc prolongation

CTCAE Grade	Instructions for osimertinib	Instructions for savolitinib	Further investigation required
CTCAE Grade 1 or Grade 2	
 No action required 	
 No action required 	
 Review concomitant treatments and comorbidities for risks of QT prolongation or risk for TdP^a
CTCAE Grade 3 (QTc interval >500 msec or >60 msec change from baseline on at least 2 separate ECGs)	
 Withhold osimertinib until QTcF interval is <481 msec within 21 days of onset, then restart osimertinib at a reduced dose of 40 mg. Dose may be resumed at 80 mg at the discretion of the investigator if the event of QTc interval is considered to be non-related to osimertinib treatment 	
 Withhold savolitinib until QTcF interval is <481 msec. If the QTcF resolves to <481 msec in 21 days, restart savolitinib at a reduced dose 	
 Review concomitant treatments and comorbidities for risks of QT prolongation or risk for TdP^a Consult with a cardiologist to validate ECG finding Ensure cardiac surveillance and take actions in accordance with clinical standards Regular ECGs performed until resolution to QTcF <481 msec

CTCAE Grade	Instructions for osimertinib	Instructions for savolitinib	Further investigation required
	
If the QTcF does not resolve to <481 msec in 21 days, discontinue osimertinib.	
If the QTcF does not resolve to <481 msec in 21 days, discontinue savolitinib	
Consult with a cardiologist for further management as clinically indicated
CTCAE Grade 4 (TdP, polymorphic ventricular, tachycardia, signs and symptoms of serious arrhythmia)	
Discontinue osimertinib	
Discontinue savolitinib	
Consult with a cardiologist for further management as clinically indicated

^a For guidance regarding potential interactions with concomitant medications known to prolong the QT interval, see Section [J 5](#).

CTCAE Common Terminology Criteria for Adverse Events; ECG Electrocardiogram; QTcF QT interval calculated using Fridericia's correction; TdP Torsades de Pointes.

In light of the potential for QT changes associated with osimertinib, electrolyte abnormalities (hypokalaemia, hypomagnesaemia, hypocalcaemia) must be corrected to within normal ranges prior to first dose and electrolyte levels monitored during study treatment.

The QTc interval prolongation potential of savolitinib 600 mg was assessed in a thorough QT study in healthy volunteers. Analysis of the data showed that it was a positive study, as the upper bounds of the 2-sided 90% CI for the mean $\Delta\Delta$ QTcF were up to 13.6 msec and 14 msec, at 4 hours and 5 hours, respectively. QTcF will be assessed frequently on triplicate ECG assessments performed at regular intervals throughout the study according to the SoA (Section [1.1](#)).

Erythema Multiforme and Stevens-Johnson Syndrome

Case reports of EM (including Erythema Multiforme Major [EMM]) and SJS have been uncommonly and rarely reported, respectively, in association with osimertinib treatment. Before initiating treatment, patients should be advised of signs and symptoms of EM/EMM and SJS. If signs and symptoms suggestive of EM/EMM develop, close patient monitoring and drug interruption or discontinuation of osimertinib should be considered. If signs and symptoms suggestive of SJS appear, osimertinib should be interrupted or discontinued immediately.

A case of SJS has been reported in temporal association with savolitinib. Patients who show symptoms or signs suggesting emerging SJS while on study treatment (eg, progressive skin rash often with blisters or mucosal lesions) must discontinue savolitinib immediately and receive appropriate treatment. If emerging SJS is suspected, re-challenge with savolitinib must be avoided.

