6.6 Dose modification

Dose modifications of one or both agents are decided by the investigator (following discussion with AstraZeneca when needed) based on the type of AEs and the known adverse drug reactions for each drug. In case a dose reduction is necessary, the study treatments will be administered as follows:

Table 8 Dose reduction for osimertinib (or placebo to osimertinib) to manage adverse events

Starting osimertinib (or placebo) dose	80 mg od (1 × 80 mg tablet once daily)
Reduced dose -1	40 mg od (1 × 40 mg tablet once daily)

od Once daily.

Table 9 Dose reduction for savolitinib to manage adverse events

Starting savolitinib dose	300 mg bid	300 mg od	600 mg od
Reduced dose -1			
Reduced dose -2			

Note: Only 2 dose reductions of savolitinib are permitted.

Bid Twice daily; od Once daily.

For guidance on dose modifications for management of AEs for osimertinib and savolitinib, see [Appendix I](#).

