7.1.1 Rechallenge

See guidance in [Appendix I](#) for circumstances under which a patient whose study treatment was temporarily interrupted due to an AE can restart treatment.

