8.4.5 Management of IP-related toxicities

8.4.5.1 Management of osimertinib-related toxicities

Potential osimertinib-related toxicities during the course of the study can be managed by interruption of the dose of osimertinib or dose reductions (see [Appendix I Section I 1](#)). Repeat dose interruptions are allowed as required. If a patient experiences a CTCAE Grade 3 (CTCAE version 5.0) and/or unacceptable toxicity, dosing will be interrupted and supportive therapy administered as required in accordance with local practice/guidelines. If the toxicity resolves or reverts to \leq CTCAE Grade 2 after 3 weeks of onset, treatment with osimertinib

may be restarted at the same dose (80 mg) or a lower dose (40 mg) using the rules in [Appendix I Section I 1](#) and with discussion and agreement with the AstraZeneca Study Team Physician as needed. There will be no individual modifications to dosing schedule in response to toxicity, only potential dose reduction or dose modification. If the toxicity does not resolve to \leq CTCAE Grade 2 after 3 weeks, then the patient should be withdrawn from the study and observed until resolution of the toxicity. Osimertinib can be dose reduced to 40 mg od: if the reduced dose of 40 mg od is not tolerable, no further dose reduction is allowed and study treatment should be discontinued. Once a dose is reduced escalation is not permitted.

Dose modifications are permitted in the management of IP-related toxicities as described in [Table 11](#) with further information being provided in [Appendix I Section I 1](#).

Dose modification guidelines for QTc prolongation are shown in [Table 12](#).

Table 11 Osimertinib dose adjustment information for adverse reactions

Target organ	Adverse reaction ^a	Dose modification
Pulmonary	ILD/pneumonitis	Permanently discontinue osimertinib
Other	Grade 3 or higher adverse reaction	Withhold osimertinib for up to 3 weeks
	If Grade 3 or higher adverse reaction improves to Grade 0 to 2 after withholding of osimertinib for up to 3 weeks	Osimertinib may be restarted at the same dose (80 mg) or a lower dose (40 mg)
	Grade 3 or higher adverse reaction that does not improve to Grade 0 to 2 after withholding for up to 3 weeks	Permanently discontinue osimertinib

^a The intensity of the clinical adverse events graded by the National Cancer Institute CTCAE Version 5.0.

ILD Interstitial lung disease.

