8.4.5.2 Management of savolitinib-related toxicities

Potential savolitinib-related toxicities during the course of the study can be managed as medically indicated and with interruption of the dose of savolitinib or dose reductions as appropriate, **unless symptoms are associated with hypersensitivity** (see [Appendix I Section I 3](#)). Repeat dose interruptions are allowed as required, taking into consideration the additional precautions for restart of savolitinib as illustrated in [Appendix I](#). For each patient the savolitinib dose can be reduced a maximum of 2 times ([Table 9](#)). No dose re-escalations are allowed.

Dose modification guidelines for QTc prolongation are shown in [Table 12](#).

Table 12 Dose modifications for QTc prolongation

NCI CTCAE Toxicity Grade	Action with savolitinib	Action with osimertinib
Grade 0, 1, or 2	None	None
Grade 3 Patients with QTcF prolongation to >500 msec on at least 2 separate ECGs If the toxicity does not resolve to QTcF <481 msec within 21 days	Hold dosing and follow algorithm below: Consult with cardiologist to validate ECG finding. Ensure cardiac surveillance and take actions in accordance with clinical standards. Regular ECGs performed until resolution to QTcF <481 msec and then restart drug at one reduced dose level.* Permanently discontinue study drug and consult with a cardiologist for further management as clinically indicated.	Hold dosing and follow algorithm below: Withhold until QTc interval is <481 msec or recovery to baseline if baseline QTc is more than 481 msec within 21 days of onset, then restart at a reduced dose (40 mg) or at 80 mg (at the discretion of the investigator). Permanently discontinue osimertinib.
Grade 4 QTcF \geq 501 or >60 msecs change from baseline and Torsade de pointes or polymorphic ventricular tachycardia or signs/symptoms of serious arrhythmia	Permanently discontinue study drug and consult with a cardiologist for further management as clinically indicated.	Permanently discontinue osimertinib.

CTCAE Common Terminology Criteria for Adverse Events; ECG Electrocardiogram; NCI National Cancer Institute; QTc corrected QT interval; QTcF corrected QT interval using Fridericia's formulas.

***For French sites only**, as per ANSM advice, the patient must remain hospitalised with continuous cardiac monitoring (ECG) until specialist advice is obtained by a cardiologist.

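### Table 11 has no cardiac row, so its generic rule would allow osimertinib to restart after heart failure that Appendix I Table 20 makes a permanent stop

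*Protocol*

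**What the plan says.** **Appendix I 1, Table 20** sets osimertinib dose adjustments under Pulmonary, Cardiac and Other. The second Cardiac entry reads "QTc interval prolongation with signs/symptoms of serious arrhythmia, symptomatic congestive heart failure", and the action is permanent discontinuation of osimertinib.

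**Section 8.4.5.1, Table 11** covers the same subject but has only Pulmonary and Other. Under Other, a Grade 3 or higher reaction leads to withholding for up to 3 weeks. The next condition is "If Grade 3 or higher adverse reaction improves to Grade 0 to 2 after withholding of osimertinib for up to 3 weeks", and then "osimertinib may be restarted at the same dose (80 mg) or a lower dose (40 mg"). A reaction that does not improve in that time leads to permanent discontinuation.

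**Links to Appendix I.** Table 11 is introduced with "Dose modifications are permitted in the management of IP-related toxicities as described in" that table, and Appendix I Section I 1 is named for further information. An earlier sentence in 8.4.5.1 makes restart subject to the rules in Section I 1, with study-physician agreement as needed. Section 6.6 says "For guidance on dose modifications for management of AEs for osimertinib and savolitinib, see" Appendix I, and Section 7.1.1 refers there "for circumstances under which a patient whose study treatment was temporarily interrupted due to an AE can restart treatment".

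**QTc rules.** Section 8.4.5.1 adds "Dose modification guidelines for QTc prolongation are shown in" Table 12. The Grade 4 stop in that table concerns "Torsade de pointes or polymorphic ventricular tachycardia or signs/symptoms of serious arrhythmia" and does not name heart failure.

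**The concern.** A permanent stop for a named cardiac event should lead to the same action wherever a site looks it up. Here the appendix table stops the drug for good, and the main-body table sends the same event through a generic rule that ends in a possible restart, including at full dose.

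The event matters to the sponsor. Table 3 classes cardiac failure as an important potential risk and an adverse event of special interest for osimertinib, and Section 8.3.13 lists changes in cardiac contractility among those events. What is at stake is re-exposure of a patient whom Table 20 would take off osimertinib permanently, at a site that works from Table 11 without turning to Table 20.

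**Working it through.** No arithmetic applies beyond counting rows. The check sets the rules side by side.

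**Step 1: rows.** Table 20 has 1 Pulmonary + 2 Cardiac + 3 Other = 6 rows. Table 11 has 1 Pulmonary + 3 Other = 4 rows. The difference, 6 − 4 = 2, is the two Cardiac rows.

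**Step 2: does Table 12 supply what is missing?** The first Cardiac row (QTc above 500 msec on at least two ECGs) has a counterpart in Table 12 at Grade 3. QTc prolongation with serious arrhythmia, in the second row, has one at Grade 4. Symptomatic congestive heart failure has none. It is the only Table 20 item absent from both Tables 11 and 12.

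**Step 3: follow symptomatic heart failure through each table**, reading Table 20 as a standalone trigger.

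| Course of the event | Table 20 | Table 11 alone |
|---|---|---|
| Grade 3 or higher, improves to Grade 0 to 2 within 3 weeks | Permanent stop | Restart at 80 or 40 mg allowed |
| Grade 3 or higher, no such improvement within 3 weeks | Permanent stop | Permanent stop |
| Below Grade 3 | Permanent stop | No row applies |

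Example: Grade 3 heart failure improves to Grade 2 on Day 14 of withholding, inside the 21-day limit. Table 20 stops osimertinib for good; Table 11 permits 80 or 40 mg. The actions are opposite only in the first line. In the third, Table 11 is silent.

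**Step 4: is heart failure a trigger in its own right in Table 20?** Two points favour this.
- Table 3 says the Appendix I guidance on cardiac contractility includes criteria for permanent discontinuation. Appendix I 1.5 offers only monitoring, so the Table 20 entry is the only heart-failure-specific stop in Appendix I 1 that can be what Table 3 means.
- None of the other QTc stop rules (Tables 12, 21 and 25, Appendix I 1.6, Section 7.1) uses heart failure to qualify a QTc event.

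**Step 5: do other lists close the gap?** No. The specific stopping criteria in Section 7.1 and the no-restart list in Appendix I 1.6 both omit heart failure.

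**The case against.** The strongest objection is that restart is already conditional on Appendix I. Section 8.4.5.1 allows it only under the rules in Section I 1, which contains Table 20, and Sections 6.6 and 7.1.1 send the reader to the same appendix. On this view a site goes wrong only by ignoring the condition in the restart sentence. The version history also records QTc details being moved out of Table 11, so that table may be meant as an abbreviated one.

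Much of this stands. A reader might infer that the protocol as a whole permits rechallenge after heart failure. The documents do not support that, because the stop exists and can be reached.

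The links do not fully remove the conflict, though. Table 11 is introduced as describing the permitted modifications, with Appendix I as further information; nothing says that Table 11 is incomplete or that Table 20 prevails. Within Section I 1, the sentence on restarting after resolution cites Table 19 (dose levels), and Table 20 is cited only for toxicity that does not resolve. A reader managing a resolved event is not led directly to the cardiac stop.

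A reader might also infer from the comma in Table 20 that heart failure merely qualifies QTc prolongation, so that the protocol leaves its meaning open. That reading is weak, for the reasons in Step 4 of the working. The shared cell may also be an artefact of reading the table from PDF. The missing row in Table 11 does not depend on that layout.

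**Conclusion.** The point holds as a limited internal conflict in a safety rule. Table 20 stops osimertinib permanently for symptomatic congestive heart failure. Table 11, used without Table 20, lets the same event restart at 80 or 40 mg if it was Grade 3 or higher and improved to Grade 0 to 2 within 3 weeks.

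It rests on two assumptions: that heart failure in Table 20 is a trigger in its own right, as Table 3 supports, and that some sites will work from the main-body table. If the sponsor meant heart failure only as a qualifier of QTc prolongation, the two tables would agree on heart failure, but Table 20 would need to say so.

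The practical risk is modest, and the documents give no expected number of events. Table 3 and Appendix I 1.5 do not regard a causal link with osimertinib as established. Exclusion criterion 3 removes patients with recent NYHA Grade 2 or higher heart failure, and Section 8.2.5 schedules ECHO or MUGA every 12 weeks. Appendix I 1 puts the local label first; its content is not in the documents, so what it would add cannot be judged. No efficacy endpoint, sample size or analysis is affected. The change should be made, because a stop rule for an event of special interest ought to read the same in both places.

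**What to change.** 1. **Table 11:** add a Cardiac row for symptomatic congestive heart failure with the action of permanently discontinuing osimertinib. Alternatively, state under Table 11 that Table 20 prevails where the two differ.
2. **Table 20 (secondary):** if the printed table does combine the two events in one cell, give heart failure its own row, or join the events with the word or.
3. **Optional:** have Appendix I 1.5 refer to the Table 20 heart-failure entry, and add heart failure to Section 7.1 as a stop for osimertinib only.

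Appendix I 1.6 need not change. It bars restart of study treatment, which Section 6 defines as osimertinib and/or savolitinib, whereas Table 20 stops osimertinib alone.

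The cost is one row or one sentence in Table 11, possibly a split cell in Table 20, and one communication to sites. Visits, sample size and analyses stay as they are.
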